5.6.3.3. Electrocardiogram

The ECG parameters that will be analyzed are heart rate (HR), PR interval, QRS interval, QT interval, and corrected QT(QTc) interval using the following correction methods: Bazett's formula (QTcB), and Fridericia's formula (QTcF).

Bazett's formula: QTcB (msec) = QT (msec) * $(HR(bpm)/60)^{0.5}$;

Fridericia's formula: QTcF (msec) = QT (msec) * $(HR(bpm)/60)^{0.33}$

If ECG measurements are repeated at a visit, they will be averaged. The averaged value will considered the 'Visit' ECG result.

Descriptive statistics of ECG parameters and change from baseline will be summarized at each scheduled time point by intervention group.

The number and percentage of participants with categorized QTc interval values will be summarized at each scheduled time point. The number and percentage of participants with categorized QTc interval increases from baseline to the maximum postbaseline value will be summarized. A shift table will be provided summarizing the shift from baseline to maximum QTc interval classification. Refer to Table 5 for summary categories.

Table 5: Criteria for Abnormal QTc Values and Changes from Baseline

QTc value (msec)	Normal QTc	nal QTc ≤450 for male, ≤470 for female	
		>450 to ≤480 for male, >470 to ≤480 for female	
		>480 to \(\leq 500\)	
		>500	
QTc change from baseline (msec)	No concern	≤30	
	Concern	>30 to ≤60	
	Clear concern	>60	

Abnormality criteria (Table 6) will be applied to baseline and postbaseline values. Postbaseline abnormalities will be compared with their corresponding baseline result:

- Treatment-emergent will be concluded if the postbaseline value is above the upper limit and the baseline value is below the upper limit (e.g., Normal or Low). The same applies to the postbaseline value being below the lower limit with the baseline value being above the lower limit (e.g., Normal or High).
- If the baseline value is missing, a postbaseline abnormality will always be considered as treatment-emergent.

The number and percentage of participants with treatment-emergent abnormal postbaseline values (relative to baseline) will be presented by intervention group over time:

ECG Parameter	Abnormally low	Abnormally high
Heart Rate (bpm)	<50 bpm	>100 bpm
PR interval (msec)	<120 msec	>200 msec
QRS interval (msec)	<60 msec	>120 msec
QT interval (msec)	<200 msec	>500 msec

Table 6: Abnormal Limits for ECG Parameters

The interpretation of the ECGs as determined by a qualified physician (investigator or qualified designee) will be displayed by the number and percentage of participants meeting the normality criteria. The interpretation will be summarized over time.

A listing of clinically relevant ECG abnormalities will also be provided.

5.6.3.4. Other Safety Parameters

5.6.3.4.1. Young Mania Rating Scale (YMRS)

The YMRS is one of the most frequently utilized rating scales to assess manic symptoms (Young 1978). The scale has 11 items and is based on the patient's subjective report of his or her clinical condition over the previous 48 hours. Additional information is based on clinical observations made during the clinical interview. The items are selected based on published descriptions of the core symptoms of mania. There are 4 items (irritability, speech, thought content, and disruptive/aggressive behavior) that are graded on a 0 to 8 scale, while the remaining 7 items are graded on a 0 to 4 scale. These 4 items are given twice the weight of the others to compensate for poor cooperation from severely ill patients. There are well-described anchor points for each grade of severity. The YMRS total score, with a range of 0 to 60, is the sum of each of the 11 individual scores, with higher total YMRS scores reflecting greater symptom severity.

Descriptive statistics of the actual values and the change from baseline to each postbaseline time point will be presented for YMRS total score and individual items by intervention group. A listing of YMRS items throughout the study for individual participants at any time point will be provided.

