On study visits 3, 4, 5, and 6, study intervention will be administered at the study site after the clinical lab and PK samples have been collected and at approximately the same time (\pm 4 hours). Study intervention will be dispensed at visits 2, 4, and 5 during this double-blind treatment period. When the participant returns to the site for visit 3, 4, 5 and 6, the participant will be administered the study intervention from the bottle dispensed from the previous visit.

Of note, on study site visits 3, 4, 5, and 6, participants will be instructed to eat breakfast at home and come to the site within 1 hour or less after completion of the meal. Inability to comply with these instructions would not constitute a protocol violation, but the participants are encouraged to comply with these instructions as closely as possible.

The well-being of the participant will be frequently tracked using a Digital Health Assessment app to monitor parameters such as, but not limited to, the pattern of sleep, energy level, and concentration level via the SAWB Questionnaire. Additionally, the Digital Health Assessment app will alert the investigator when a participant has indicated that their depression is 'much worse' or 'very much worse' when answering weekly questions on depression.

The SHAPS will be administered once at baseline (pre-dose) and once at the end of the double-blind treatment phase (after the final dose). Participants will complete the PROMIS - Ability to Participate in Social Roles and Activities and the PHQ-9 at baseline and once weekly, and the GAD-7 every two weeks. As per SoA, the self-rating instruments will be administered at clinic visits or at home. For self-rating instruments completed at home on paper, participants should complete these scales before the next clinic visit and participants will receive notifications from the Digital Health Assessment app on their mobile phones as reminders to complete these paper instruments.

Key safety assessments will include the monitoring of adverse events, physical examinations, vital signs (e.g., blood pressure, pulse/heart rate, body temperature), electrocardiogram (ECG), clinical laboratory tests, emergence of mania (YMRS), and suicidal ideation (C-SSRS).

In addition, blood samples for PK, biomarker assessment, hormones (males only), and pharmacogenomics (general SNPs and RNA) will be collected as per the SoA and use of concomitant medication will be recorded.

Follow-up Examination

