An additional optional pharmacogenomic blood sample will be collected from enrolled participants on Day 1 to identify genetic factors that may influence the PK, PD, efficacy, safety and/or tolerability of JNJ-55308942 and to identify genetic factors associated with BD. If collection on Day 1 is not feasible, it can be collected on any other visit during the double-blind treatment phase.

SAFETY EVALUATIONS

Adverse events (AEs) will be reported by the participant (or, when appropriate, by a caregiver, surrogate, or the participant's legally acceptable representative) from obtaining the screening informed consent through the day of last dose plus 30 days. There are no AEs of special interest.

The following safety assessments will be performed: physical examination, body weight, vital signs (including oral, tympanic or temporal temperature, blood pressure, pulse/heart rate and respiratory rate), 12-lead electrocardiogram (ECG), urine drug testing, alcohol breath test, pregnancy testing (female participants only), hormones, and clinical labs (hematology, chemistry panel and urinalysis) as per SoA. In addition, serology and hemoglobin A1c (HbA1c) assessments will be performed at screening only.

Emergence of mania will be assessed using the YMRS at each visit.

Emergence of suicidal ideation will be assessed using the C-SSRS at screening and during each visit. The Digital Health Assessment app will alert the investigator when a participant has indicated that the depression is 'much worse' or 'very much worse' when answering weekly questions on depression.

STATISTICAL METHODS

Sample Size

The estimated sample size of 164 participants (82 participants per group) was determined based on the assumption of an effect size of at least 0.45 for the MADRS total score (difference in mean change from baseline at Week 6 between the JNJ-55308942 and placebo groups of 3.9 units with a standard deviation of 8.6). This is considered to be a clinically relevant difference in a population with BD types I or II. The standard deviation of 8.6 in the change in MADRS total score from baseline is a reasonable assumption based on data in a published phase 3 study of quetiapine in BD type I and type II depression (Calabrese 2005). Power is set at 90%, with a 1-sided alpha of 0.10 and a 6-week drop-out rate of 20%. The estimated number of completers to be included in the primary analysis is 132.

Efficacy Analyses

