Descriptive statistics of body temperature, pulse/heart rate, supine blood pressure, and respiratory rate values and changes from baseline will be summarized at each scheduled time point. The percentage of participants with values outside clinically relevant limits will be summarized.

Physical Examination

Abnormalities observed during the physical examination will be summarized and listed by treatment group at each scheduled time point.

Young Mania Rating Scale (YMRS)

Exploratory analyses will be performed for changes from baseline in YMRS total score and for changes from baseline in individual YMRS items by treatment group for all participants receiving at least 1 dose of study intervention. Details will be provided in the SAP.

Columbia Suicide Severity Rating Scale (C-SSRS)

Results from the C-SSRS will be tabulated by treatment group for all participants receiving at least 1 dose of study intervention.

[figure not shown]
Interim analysis

No interim analysis is planned.

It may be recommended that an unblinded data review needs to be performed by an independent reviewer (e.g., data review committee) if deemed critical by the Janssen clinical team. Committee membership responsibilities, authorities, and procedures will be documented in a charter.

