5. STATISTICAL ANALYSES

5.1. General Considerations

Continuous variables will be summarized by descriptive statistics including the number of participants (N), mean, standard deviation (SD), median, and range (minimum; maximum) unless otherwise specified. Categorical variables will be summarized by frequency counts and percentages.

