- TEAEs by system organ class and preferred term
- Treatment-emergent serious adverse events (SAEs) by system organ class and preferred term
- TEAEs leading to discontinuation of study intervention by system organ class and preferred term
- TEAEs by system organ class, preferred term, and worst severity
- TEAEs by system organ class, preferred term, and relationship to study intervention.

In addition to the summary tables, listings will be provided for participants who had:

- AEs
- SAEs
- AEs leading to discontinuation of study intervention

A listing of participants who died will be provided.

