5.6.3.4.2. Columbia Suicide Severity Rating Scale (C-SSRS)

The C-SSRS is a low-burden measure of the spectrum of suicidal ideation and behavior that was developed to assess severity and track suicidal events through any intervention (Posner 2007). It is a clinical interview providing a summary of both suicidal ideation and behavior that can be

administered during any evaluation or risk assessment to identify the level and type of suicidality present. The C-SSRS has been used frequently in clinical studies and is a validated, standard measure for suicidal ideation assessment. Using the C-SSRS, the outcomes will be categorized using the scoring for the 11 categories:

Suicid	Suicidal Ideation (1-5)		
1	Wish to be dead		
2	Non-specific active suicidal thoughts		
3	Active suicidal ideation with any methods (not plan) without intent to act		
4	Active suicidal ideation with some intent to act, without specific plan		
5	Active suicidal ideation with specific plan and intent		
Suicid	Suicidal Behavior (6-10)		
6	Preparatory acts or behavior		
7	Aborted attempt		
8	Interrupted attempt		
9	Actual attempt		
10	Suicide		
Non-s	Non-suicidal self-injurious behavior (11)		
11	Non-suicidal self-injurious behavior		

If no events qualify for a score of 1 to 10, a score of 0 will be assigned (0 = "no suicidal ideation or behavior that can be assessed on the basis of C-SSRS"). A participant with a score of 11 will be considered as not having suicidal ideation or behavior.

Shifts from baseline to the maximum postbaseline score pertaining to suicidal ideation or suicidal behavior (i.e., scores 1 to 10) will be summarized by intervention group.

The maximum score (of scores 1 to 10) assigned to each participant will be grouped into one of three broad categories: No suicidal ideation or behavior (0), Suicidal ideation (1-5), and Suicidal behavior (6-10). Shifts from baseline to the maximum postbaseline category will be summarized by intervention group.

Frequency distribution of the scores for the 11 categories will be provided at each time point by intervention group.

A listing of C-SSRS items throughout the study for participants with Suicidal Ideation or Behavior at any time point will be provided.

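### Emergence of mania is a key safety question, but the SAP plans no count by arm of participants with a marked post-baseline rise on the YMRS

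*SAP*

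**What the plan says.** Protocol 1.1 (Synopsis, Safety Evaluations) states: "Emergence of mania will be assessed using the YMRS at each visit". Sections 1.1 and 4.1 both list the YMRS among the key safety assessments. On analysis, the synopsis says "Exploratory analyses will be performed for changes from baseline in YMRS total score" and for the individual items, and leaves the details to the SAP. No YMRS threshold is mentioned there.

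SAP 5.6.3.4.1 supplies those details: "Descriptive statistics of the actual values and the change from baseline to each postbaseline time point will be presented for YMRS total score" and for individual items, by intervention group. SAP 5.1 defines descriptive statistics as the number of participants, "mean, standard deviation (SD), median, and range (minimum; maximum) unless otherwise specified". Section 5.6.3.4.1 adds: "A listing of YMRS items throughout the study for individual participants at any time point will be provided".

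Two other parts of the plan bear on this. SAP 5.6.2 tabulates "TEAEs by system organ class and preferred term" with numbers and percentages by group, so a manic episode recorded as an adverse event is counted. Exclusion criterion 4 (Protocol 5.2) bars entry with a YMRS above 12. That is the only place where 12 appears as a YMRS limit.

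**The concern.** Participants enter with low YMRS scores, so emergent mania would appear as a large rise in a few people, not as a shift of the whole arm. The useful summary of such an event is how many people in each arm had it. A mean or median at each visit cannot show that. A maximum at each visit shows that at least one person scored high, but not how many. A listing leaves the reader to count by hand.

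The documents treat affective switch as important. Protocol 4.2 gives avoiding a switch as one reason for barring antidepressants, and Protocol 8.7.4 lists mania as an anticipated event. Protocol 2.3.1 says the drug has not been given to humans for more than 10 days, nor to patients with bipolar depression. A reader of the study report will want the number of switches by arm, and the plan does not produce it from the scale chosen to measure it.

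**Working it through.** **1. The plan's own figures.** The documents give no expected switch rate, no SD for YMRS change and no sample size argument for the YMRS. The only figure borrowed here is 82 per arm, which reproduces from SAP 3: n = 2 × (1.2816 + 1.2816)² / 0.45² = 64.9, so 65 per arm; 65 / 0.80 = 81.25, so 82 per arm and 164 in total.

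**2. How the SAP treats its safety measures.**

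| Measure | Section | Categorical or worst-value summary by arm? |
|---|---|---|
| Vital signs | 5.6.3.2 | Yes: incidence of treatment-emergent abnormalities |
| QTc | 5.6.3.3 | Yes: categories, and shift to maximum post-baseline class |
| C-SSRS | 5.6.3.4.2 | Yes: "Shifts from baseline to the maximum postbaseline category will be summarized by intervention group" |
| YMRS | 5.6.3.4.1 | No: statistics by visit and a listing |

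No reason is given for the difference.

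**3. How far a few switches move the mean.** The shift in an arm mean is k × R / n, for k participants each rising R points. With n = 82 and assumed k and R:

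- k = 1, R = 12: 12 / 82 = 0.15 points
- k = 4, R = 12: 48 / 82 = 0.59 points
- k = 4, R = 20: 80 / 82 = 0.98 points

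The 80% interval half-width for a difference in means is 1.2816 × SD × √(2/82). For an assumed SD of change of 3, 4 or 5 it is 0.6, 0.8 or 1.0 points. Four switches of 12 points in one arm and none in the other would therefore sit inside or at the edge of that interval.

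**4. What a count would show.** With 82 per arm and a Wald 80% interval:

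- 4 v 0: difference 4 / 82 = 4.9% (1.8 to 7.9); 1-sided Fisher p = 0.06
- 4 v 1: difference 3 / 82 = 3.7% (0.2 to 7.1); 1-sided Fisher p = 0.18

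The count states the finding directly. In the second case the Wald interval excludes zero while the exact test is well above 0.10, so Wald is too narrow for counts this small.

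**5. What the count can miss or misclassify.**

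- *Baseline.* SAP Appendix 2 (6.2) accepts some post-dose Day 1 YMRS values as baseline, and Appendix 4 (6.4) allows for participants who entered without meeting the criteria. A baseline above 12 is possible, so the definition needs a baseline condition.
- *Schedule.* The Schedule of Activities (Protocol 1.3) and SAP Table 2 have no YMRS at the follow-up or early withdrawal visit, which does not fit the synopsis wording. The scale covers the previous 48 hours, and the last three treatment-phase YMRS assessments (Days 15, 29 and 43) are two weeks apart. A participant who switches and withdraws between visits may have no raised score on record.
- *Visit windows.* SAP 5.1.2 keeps only the visit closest to target in each window and leaves the others out of summaries. An extra YMRS taken during an episode could therefore be dropped from the statistics by visit, including the maximum.

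**The case against.** The best defence is that the plan is not blind to mania. It reports medians and maxima, summarises all 11 items and lists individual scores. Adverse events are counted by preferred term and arm, with separate tables for serious events and for those leading to discontinuation. Protocol 8.7.4 adds periodic aggregate review of anticipated events, mania among them. The protocol calls the YMRS analyses exploratory, and in an early study case-level review is a reasonable tool. All of this stands, and it rules out saying that the YMRS is summarised by mean change alone. It does not supply a count by arm from the scale: adverse event counts depend on the investigator reporting the event, and a listing is not a table.

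A reader might infer three stronger points that the documents do not support.

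- *That above 12 is the protocol's definition of a manic switch.* It is an entry limit only. A rise from 12 to 13 would count as a case, so its use must be stated as a descriptive convention.
- *That every post-baseline value above 12 is treatment-emergent.* The post-dose baselines and possible entry deviations prevent this.
- *That testing the proportion would be reliably more powerful than testing the mean.* No YMRS test is planned, and every switch rate is an assumption. At 82 per arm and 1-sided 0.10, exact Fisher power is 0.36 for 1% v 5%, 0.33 for 2% v 6%, 0.55 for 2% v 8% and 0.59 for 3% v 10%. At an assumed 8% v 1%, simulated power was about 0.42 to 0.62 for an observed score above 12 and about 0.48 to 0.54 for the mean, depending on the assumed baseline scores. Neither is consistently better.

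**Conclusion.** The concern holds as a gap in reporting. For a named key safety assessment, the SAP gives statistics by visit and a listing, but no count by arm of participants with a marked post-baseline elevation, while three neighbouring safety measures get a categorical or worst-value summary.

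The dilution argument rests on assumed inputs: 1 to 4 switches among 82, each of 12 to 20 points, move the arm mean by 0.15 to 0.98 points, against a half-width of 0.6 to 1.0 for an SD of 3 to 5. The absence of a count is read directly from the SAP and needs no assumption. The benefit of the change is a direct count of cases by arm; it carries no claim of adequate power or of a fixed power gain over the mean.

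**What to change.** Add to SAP 5.6.3.4.1 one descriptive table in the safety analysis set:

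- n (%) by arm of participants with baseline YMRS of 12 or less and worst post-baseline YMRS above 12, with a statement that this cut-off is the entry limit used descriptively and not a protocol definition of switch;
- the worst value taken over all post-baseline assessments, including those not selected by the visit-window rule;
- the risk difference with an 80% CI, preferably by a score-type method suited to small counts;
- participants with baseline above 12, and those with no post-baseline YMRS, counted separately;
- alongside, n (%) by arm with a treatment-emergent adverse event of mania or hypomania, with a note that the two counts are to be read together because the YMRS count can miss participants who switch and withdraw between visits.

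Separately, reconcile the synopsis statement on when the YMRS is assessed with the Schedule of Activities and SAP Table 2.

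The cost is a few SAP sentences and one table from data already collected. Nothing changes for participants or sites, and the existing summaries and listing stay.

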5.6.3.4.2. Columbia Suicide Severity Rating Scale (C-SSRS)

The C-SSRS is a low-burden measure of the spectrum of suicidal ideation and behavior that was developed to assess severity and track suicidal events through any intervention (Posner 2007). It is a clinical interview providing a summary of both suicidal ideation and behavior that can be

administered during any evaluation or risk assessment to identify the level and type of suicidality present. The C-SSRS has been used frequently in clinical studies and is a validated, standard measure for suicidal ideation assessment. Using the C-SSRS, the outcomes will be categorized using the scoring for the 11 categories:

Suicid	Suicidal Ideation (1-5)		
1	Wish to be dead		
2	Non-specific active suicidal thoughts		
3	Active suicidal ideation with any methods (not plan) without intent to act		
4	Active suicidal ideation with some intent to act, without specific plan		
5	Active suicidal ideation with specific plan and intent		
Suicid	Suicidal Behavior (6-10)		
6	Preparatory acts or behavior		
7	Aborted attempt		
8	Interrupted attempt		
9	Actual attempt		
10	Suicide		
Non-s	Non-suicidal self-injurious behavior (11)		
11	Non-suicidal self-injurious behavior		

If no events qualify for a score of 1 to 10, a score of 0 will be assigned (0 = "no suicidal ideation or behavior that can be assessed on the basis of C-SSRS"). A participant with a score of 11 will be considered as not having suicidal ideation or behavior.

Shifts from baseline to the maximum postbaseline score pertaining to suicidal ideation or suicidal behavior (i.e., scores 1 to 10) will be summarized by intervention group.

The maximum score (of scores 1 to 10) assigned to each participant will be grouped into one of three broad categories: No suicidal ideation or behavior (0), Suicidal ideation (1-5), and Suicidal behavior (6-10). Shifts from baseline to the maximum postbaseline category will be summarized by intervention group.

Frequency distribution of the scores for the 11 categories will be provided at each time point by intervention group.

A listing of C-SSRS items throughout the study for participants with Suicidal Ideation or Behavior at any time point will be provided.

